#### **10.2.1. Adverse Events of Special Interest**

AEs of special interest - allergic reactions (including hypersensitivity and anaphylaxis), pancreatitis, and thrombosis - will be summarized by dose level of RC-P, route of administration (IM or IV), and patients subgroups specified in [Section 7.4](#). The list of PTs used to search each AEs of special interest, reviewed by Jazz Drug Safety & Pharmacovigilance, is provided in [Appendix II](#).

#### **10.3. Laboratory Assessments**

Baseline value, post-baseline value, and changes from baseline value for all hematology, coagulation, and chemistry parameters will be summarized by dose level of RC-P and route of administration (IM or IV) using descriptive statistics.

#### **10.4. Vital Signs**

Baseline value, post-baseline value, and changes from baseline value for all vital signs (systolic and diastolic blood pressure, pulse rate, respiratory rate) and body temperature will be summarized by dose level of RC-P and route of administration (IM or IV) using descriptive statistics.

#### **10.5. Other Safety Endpoints**

A data listing will be provided for patients experiencing pregnancy during the study.

Jazz Pharmaceuticals Ireland Limited  
Statistical Analysis Plan – Protocol JZP458-201

## 11. PHARMACOKINETIC/PHARMACODYNAMIC ANALYSES

The summary and listings of RC-P PK (SAA and serum asparaginase concentration levels) and PD (asparagine and glutamine concentrations) measurements will be provided. Descriptive statistics including number of patients, mean, SD, median, min, max, coefficient of variation (CV), geometric mean, and geometric standard deviation will be used to summarize PK and PD data by time, dose level, Course, and route of administration (IM or IV), as appropriate. Proportion of patients with NSAA  $\geq 0.1$  and  $\geq 0.4$  IU/mL by time will also be summarized for SAA data.

Individual and/or summary figures of SAA-time or enzyme concentration-time profiles in serum may be provided. Individual and/or summary figures of SAA versus PD profiles may also be provided.

Statistical summaries and displays will be based on scheduled sampling times unless significant deviations occur (outside of the specified time windows in Appendix 2 in protocol). Differences between scheduled and actual sampling times will be listed for all patients.

RC-P SAA data will be used in a population PK analysis. A population PK model will be used to characterize the RC-P PK profiles in patients with ALL/LBL following hypersensitivity to *E. coli*-derived asparaginases, and to explore exposure-response correlations. Results from the population PK analysis will be reported separately from the CSR, in a standalone document.

Jazz Pharmaceuticals Ireland Limited  
Statistical Analysis Plan – Protocol JZP458-201

## **12. IMMUNOGENICITY**

The summary of immunogenicity results will be provided by dose level, Course, and route of administration (IM or IV) as appropriate. Immunogenicity results will be also listed as positive or negative for the presence of ADA for each patient by dose level, Course, and route of administration (IM or IV), as appropriate. In addition, for all ADA positive samples, titer values will be provided as a quantification measurement of antibodies.

For those with positive ADA results, individual profile may be provided to present ADA and hypersensitivity onset time along with each course start time. Boxplots of serum asparaginase activity levels by ADA status may also be provided.

Jazz Pharmaceuticals Ireland Limited  
Statistical Analysis Plan – Protocol JZP458-201

### **13. COVID-19**

Data identifying missed visits, missed assessments, study drug discontinuation, and/or study participation termination due to COVID-19 will be captured either in EDC (study drug discontinuation and study participation termination) or protocol deviation log (missed visits and missed assessments). The collected data will specify if the study disruption was due to acquiring COVID-19 or due to other COVID-19 restrictions.

A summary of major protocol deviations due to COVID-19 will be provided. A listing of all disruptions due to COVID-19 will be provided (i.e. missed visits, missed assessments, study drug discontinuation, and study participation termination).

## APPENDIX I. DATE IMPUTATION RULES

### Incomplete Adverse Event Onset Date

If *year* is missing (or completely missing): set to the date of first dose.

If (*year* is present and *month* and *day* are missing) or (*year* and *day* are present and *month* is missing):

If *year* = year of first dose: set the date to the first dose date.

If *year* < year of first dose: set *month* and *day* to December 31st.

If *year* > year of first dose: set *month* and *day* to January 1st.

If *month* and *year* are present and *day* is missing:

If *year* = year of first dose, and:

If *month* = month of first dose: set *day* to day of first dose.

If *month* < month of first dose: set *day* to last day of *month*.

If *month* > month of first dose: set *day* to 1st day of *month*.

If *year* < year of first dose: set *day* to last day of month.

If *year* > year of first dose: set *day* to 1st day of month.

For all other cases: set to date of first dose.

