6.7.6.5. Adverse Event Recording and Reporting

The Investigator must record all AEs that occur from the time written informed consent is obtained until 30 days after the patient's last dose of the last course of RC-P, regardless of their relationship to study drug.

In addition, any SAE assessed as related to study drug by the Investigator that occurs more than 30 days after the patient's last dose of the last course of RC-P, must be reported as described below.

Serious AEs must be reported to the Sponsor or its designee using an SAE Reporting Form within 24 hours of first knowledge of the event by study site personnel. The reporting form and contact information for submission of the form, will be provided to the study sites separately.

The reporting form must be completed as thoroughly as possible before transmittal to the contact provided on the form. The Investigator must provide his/her assessment of causality to the study drug and study procedure at the time of an initial SAE report. If the Investigator's assessment of causality changes after the initial report, it must be provided as follow-up information to the Sponsor.

Other Reportable Experiences:

Overdose, (defined as any dose administered or received that was higher than the intended dose), medication errors (defined as any unintentional error in the dispensing or administration of the study drug), and misuse of the study drug are considered reportable experiences and should be reported by study site personnel on an Other Reportable Experience Form. The form, and contact information for submission of the form, will be provided to the study sites separately.

If any overdose, medication error or misuse of the study drug results in an AE this must be recorded, and if this AE is serious it must also be reported as described above.

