### 10.2. Adverse Events

AEs recorded in the case report form will be coded to system organ class (SOC) and preferred term (PT) using the Medical Dictionary for Regulatory Activities (MedDRA 22.1). The investigator will assess the relatedness of each AE to study drug. The severity of AEs will be recorded using the Common Terminology Criteria for Adverse Events (CTCAE 5.0).

At a minimum, the investigator must record all AEs that occur from the time written informed consent is obtained until screen failure if applicable, or 30 days after the patient's last dose of the last course of RC-P, regardless of their relationship to study drug. Any serious AE (SAE) assessed as related to study drug by the investigator that occurs more than 30 days after the patient's last dose of the last course of RC-P should be reported regardless of time after study termination.

A treatment-emergent adverse event (TEAE) is defined as any event with onset date on or after Study Day 1 through the end of the study or any ongoing event that worsens in severity after Study Day 1 through the end of the study. Only TEAEs with the onset date through the end of the AE reporting period will be included in summary tables unless otherwise specified. For the purpose of calculating treatment emergence, incomplete onset dates will be imputed as detailed in [Appendix I](#).

AEs are graded by the investigator as Grade 1 (mild), Grade 2 (moderate), Grade 3 (severe or medically significant but not immediately life-threatening), Grade 4 (life-threatening consequences), or Grade 5 (Death related to AE). The severity grade of events for which the investigator did not record severity will be categorized as "missing" for tabular summaries and data listings, and will be considered the least severe for the purposes of sorting for data presentation.

Treatment-related AEs are those for which the investigator answers "Yes" to the question "Was this adverse event related to study treatment?" in the eCRF. Events for which the investigator did not record relationship to study treatment will be considered related to study treatment for summary purpose. Data listings will show treatment-relationship as missing. AEs for which "Yes"

Jazz Pharmaceuticals Ireland Limited  
Statistical Analysis Plan – Protocol JZP458-201

is marked for question “Was this adverse event related to study procedure?” in eCRF will be identified and included in AE listing.

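### In four branches, SAP Appendix I moves an incomplete AE onset to the first-dose date without reading the stop date, so an AE known to have ended before RC-P can count as treatment-emergent

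*SAP*

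**What the plan says.** **The imputation rule.** SAP Appendix I, under the rules for incomplete AE onset dates, leads to the first-dose date in four situations:

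- the year "is missing (or completely missing): set to the date of first dose";
- the month is missing and the known year equals the "year of first dose: set the date to the first dose date";
- only the day is missing, the year is that of first dose, and the month equals the "month of first dose: set *day* to day of first dose";
- the fallback: "For all other cases: set to date of first dose".

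The remaining branches do not. A known earlier year without a month goes to 31 December of that year. A known earlier month goes to its last day. A later month or year goes to its first day.

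**The use of the imputed date.** SAP Section 10.2 says that a TEAE "is defined as any event with onset date on or after Study Day 1 through the end of the study", or an ongoing event that worsens after that day. It links the two parts directly: "For the purpose of calculating treatment emergence, incomplete onset dates will be imputed as detailed in" Appendix I. SAP Section 7.2.1 makes Study Day 1 the date of the first RC-P dose.

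**The data available.** Under Protocol Section 6.7.6.5 the investigator "must record all AEs that occur from the time written informed consent is obtained until 30 days" after the last dose of the last course. Screening can last 28 days (Protocol Section 3.4). Resolution dates are recorded (Protocol Section 6.7.6.6), and AE stop dates appear in the SAP listings (Section 10.2).

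**The concern.** Setting an uncertain onset to the first-dose date is a sensible cautious default when nobody can tell whether the event began before or after treatment. A stop date before first dose removes that uncertainty: the event was over before any RC-P was given. In the four branches above the rule still assigns it an onset on the day of first dose. The record then has an onset later than its end, and a pre-treatment event enters the TEAE tables.

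The occurrence of TEAEs is the primary safety endpoint (SAP Section 4.2.1), and the AE of special interest summaries cover allergic reactions, pancreatitis and thrombosis (SAP Section 10.2.1). Section 10.2 also counts an event with no recorded relationship as treatment-related in summaries, so a poorly documented Screening event could appear in both the TEAE and the related-TEAE tables.

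Pre-dose records with stop dates will exist. Conditions arising after consent are AEs rather than medical history (Protocol Section 6.2). In Cohort 1, each change in severity from consent through Course 1 closes one AE record and opens another (Protocol Section 6.7.6.2).

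Nothing elsewhere in the SAP repairs this. Section 8.5 says that medications, in the same way as AEs, are classified after incomplete start and end dates have been considered, and it refers to Appendix I. That appendix has end-date rules for medications but none for AEs.

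**Working it through.** The plan states no figure on this point, so the check is of the logic, followed by the size of one misclassified event.

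**Step 1: apply the rules to a test case.** Take a first dose on 22 June 2020 and an AE with a recorded stop date of 15 June 2020 (invented dates, for illustration). Classify with Appendix I, then Section 10.2.

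| Onset as recorded | Imputed onset | TEAE under the SAP? | Onset after recorded stop? |
|---|---|---|---|
| Completely missing | 22 Jun 2020 | Yes | Yes |
| 2020 | 22 Jun 2020 | Yes | Yes |
| Jun 2020 | 22 Jun 2020 | Yes | Yes |
| May 2020 | 31 May 2020 | No | No |
| 2019 | 31 Dec 2019 | No | No |

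The first three rows are wrong, because the event ended seven days before dosing. The last two are right. With a stop-date check, all five are classified as not treatment-emergent.

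**Step 2: how often a pre-dose onset falls into these branches.** Assume that the true onset is equally likely on each of the 28 days before dosing, and take every first-dose date in 2020 and 2021: 731 × 28 = 20,468 combinations.

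- *Day missing.* The onset moves if it lies in the month of first dose. For a first dose on day d of the month, min(d − 1, 28) of the 28 days qualify. Summed over a month this gives 462 for 31 days, 434 for 30, 406 for 29 and 378 for 28. Over two years: 14 × 462 + 8 × 434 + 406 + 378 = 10,724, and 10,724 / 20,468 = 52%.
- *Month and day missing.* The onset moves unless it lies in the previous calendar year. That exception covers 28 + 27 + … + 1 = 406 combinations per year, or 812 in all: 1 − 812 / 20,468 = 96%.
- *Date completely missing.* 100%.

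These are shares of pre-dose AEs that already have an incomplete onset, before any stop-date check. They are not error rates: the documents do not say how many onsets will be incomplete, or how many of those AEs will have a known pre-dose stop date.

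**Step 3: size of one event.** Section 10.2 counts a patient once per preferred term, so one event adds at most one patient to a row. Section 10 tabulates safety by dose level and route, so the denominator varies:

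- final IM dose at the planned size: 1/98 = 1.0 percentage point;
- one Part A Cohort 1 subcohort of 13: 1/13 = 7.7 points;
- a Part B cohort of 6: 1/6 = 17 points.

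**The case against.** The strongest reply is that the error needs several things together: an AE that starts after consent and ends before dosing, an onset incomplete in one of the four branches, and a stop date good enough to show that it preceded dosing. AEs are reviewed at Screening and at dosing visits (Protocol Appendix 1), the data undergo programmed and manual checks (Protocol Section 9), and the listings show onset beside stop date. The bias is conservative, there is no formal safety testing (SAP Section 10), and efficacy is untouched. A programming specification might well add the exception anyway. All of this stands as a limit on importance. It does not remove the defect, because the SAP as written prescribes a result that contradicts recorded data.

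Three stronger readings are tempting, and the documents do not support them.

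- *All partial onsets are moved to first dose.* They are not; a known earlier month or year stays before dosing.
- *The E. coli asparaginase reaction that qualified the patient could be counted as RC-P toxicity.* That reaction is an entry condition and would normally precede consent. Protocol Section 6.2 places it in medical history, so it should not reach Appendix I.
- *A misdated event could trip a stopping limit.* One extra patient would move pancreatitis or thrombosis from 3/32 (9.4%) to 4/32 (12.5%), or from 5/51 (9.8%) to 6/51 (11.8%), across the 10% limit. But neither document says that these incidences come from imputed TEAE data, and the allergic-reaction limit counts only reactions related to RC-P.

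**Conclusion.** The point holds as a minor defect in a stated rule. In four branches of Appendix I, an AE with a recorded stop date before first dose becomes a TEAE with an onset after its own end. The effect is one-sided: it can only raise TEAE counts. Each affected event adds up to one patient to a row, which is small at the final IM dose and visible in the small dose-level columns. The figure of 1.0 point is not a general ceiling, since it applies only to the planned 98 patients.

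The total effect cannot be computed from the documents and is probably small. The conclusion rests on the text of Appendix I and Section 10.2 being programmed as written. It does not depend on the uniform-onset assumption, which serves only to show that the affected branches cover much of the Screening period.

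**What to change.** Add to SAP Appendix I, under incomplete AE onset dates:

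> The onset is imputed to the first-dose date only if the AE stop date is missing, the event is ongoing, or the stop date (taken at its latest possible value if partial) is on or after the first dose. Otherwise the onset is imputed no later than the stop date, and the AE is not treatment-emergent.

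This also settles how partial AE stop dates are treated, which Appendix I now leaves open although Section 8.5 implies a rule exists. For example, with first dose on 22 June 2020, a stop date of June 2020 has 30 June as its latest value, so the cautious default still applies.

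The cost is one short SAP addition and one program condition. No data collection, sample size or efficacy analysis changes.

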### Incomplete Concomitant Medication Start Date

If *year* is missing (or completely missing): do not impute.

If (*year* is present and *month* and *day* are missing) or (*year* and *day* are present and *month* is missing):

Set *month* and *day* to January 1st.

If *year* and *month* are present and *day* is missing:

Set *day* to 1st day of month.

Jazz Pharmaceuticals Ireland Limited  
Statistical Analysis Plan – Protocol JZP458-201

Incomplete Concomitant Medication End Date

Do not impute if Ongoing Flag is checked.

If *year* is missing (or completely missing): do not impute.

If (*year* is present and *month* and *day* are missing) or (*year* and *day* are present and *month* is missing):

Set *month* and *day* to December 31st.

If *year* and *month* are present and *day* is missing:

Set *day* to last day of the month.

Incomplete Subsequent Anti-Leukemic/Cancer Therapy Start Date

Assumption: Anti-Cancer therapies reported on the Subsequent Anti-Leukemic/Cancer Therapy eCRF.

If *year* is missing (or completely missing): set to date of last dose of study treatment + 1

If (*year* is present and *month* and *day* are missing) or (*year* and *day* are present and *month* is missing):

If *year* > year of the last dose: Set *month* and *day* to January 1st.

If *year* = year of the last dose: Set *month* and *day* to date of last dose of study treatment + 1

If *year* and *month* are present and *day* is missing:

Set *day* to 1st day of month if the resulting imputed date is greater than date of last dose. Otherwise set the imputed date to date of last dose + 1

NOTE: If progressive disease/Relapse date is available and after date of last dose, replace last dose of study drug with progressive disease/Relapse date for imputation algorithm given in this section.

Jazz Pharmaceuticals Ireland Limited  
Statistical Analysis Plan – Protocol JZP458-201

## **APPENDIX II. PTS USED TO SEARCH AES OF SPECIAL INTEREST**

### **List of PTs under the narrow SMQs for Hypersensitivity**

Acquired C1 inhibitor deficiency  
Acute generalised exanthematous pustulosis  
Administration related reaction  
Administration site dermatitis  
Administration site eczema  
Administration site hypersensitivity  
Administration site rash  
Administration site recall reaction  
Administration site urticaria  
Administration site vasculitis  
Allergic bronchitis  
Allergic colitis  
Allergic cough  
Allergic cystitis  
Allergic eosinophilia  
Allergic gastroenteritis  
Allergic hepatitis  
Allergic keratitis  
Allergic oedema  
Allergic otitis externa  
Allergic otitis media  
Allergic pharyngitis  
Allergic reaction to excipient  
Allergic respiratory disease  
Allergic respiratory symptom  
Allergic sinusitis  
Allergic stomatitis  
Allergic transfusion reaction  
Allergy alert test positive  
Allergy test positive  
Allergy to immunoglobulin therapy  
Allergy to surgical sutures  
Allergy to vaccine  
Anal eczema  
Anaphylactic reaction  
Anaphylactic shock  
Anaphylactic transfusion reaction

Jazz Pharmaceuticals Ireland Limited  
Statistical Analysis Plan – Protocol JZP458-201

Anaphylactoid reaction  
Anaphylactoid shock  
Anaphylaxis treatment  
Angioedema  
Antiallergic therapy  
Antiendomysial antibody positive  
Anti-neutrophil cytoplasmic antibody positive vasculitis  
Application site dermatitis  
Application site eczema  
Application site hypersensitivity  
Application site rash  
Application site recall reaction  
Application site urticaria  
Application site vasculitis  
Arthritis allergic  
Aspirin-exacerbated respiratory disease  
Atopic cough  
Atopy  
Blepharitis allergic  
Blood immunoglobulin E abnormal  
Blood immunoglobulin E increased  
Bromoderma  
Bronchospasm  
Catheter site dermatitis  
Catheter site eczema  
Catheter site hypersensitivity  
Catheter site rash  
Catheter site urticaria  
Catheter site vasculitis  
Chronic eosinophilic rhinosinusitis  
Chronic hyperplastic eosinophilic sinusitis  
Circulatory collapse  
Circumoral oedema  
Circumoral swelling  
Conjunctival oedema  
Conjunctivitis allergic  
Contact stomatitis  
Contrast media allergy  
Contrast media reaction  
Corneal oedema  
Cutaneous vasculitis

Jazz Pharmaceuticals Ireland Limited  
Statistical Analysis Plan – Protocol JZP458-201

Dennie-Morgan fold  
Dermatitis  
Dermatitis acneiform  
Dermatitis allergic  
Dermatitis atopic  
Dermatitis bullous  
Dermatitis contact  
Dermatitis exfoliative  
Dermatitis exfoliative generalised  
Dermatitis herpetiformis  
Dermatitis infected  
Dermatitis psoriasiform  
Device allergy  
Dialysis membrane reaction  
Distributive shock  
Documented hypersensitivity to administered product  
Drug eruption  
Drug hypersensitivity  
Drug provocation test  
Drug reaction with eosinophilia and systemic symptoms  
Eczema  
Eczema infantile  
Eczema nummular  
Eczema vaccinatum  
Eczema vesicular  
Eczema weeping  
Encephalitis allergic  
Encephalopathy allergic  
Eosinophilic granulomatosis with polyangiitis  
Epidermal necrosis  
Epidermolysis  
Epidermolysis bullosa  
Epiglottic oedema  
Erythema multiforme  
Erythema nodosum  
Exfoliative rash  
Eye allergy  
Eye oedema  
Eye swelling  
Eyelid oedema  
Face oedema

Jazz Pharmaceuticals Ireland Limited  
Statistical Analysis Plan – Protocol JZP458-201

Fixed eruption  
Giant papillary conjunctivitis  
Gingival oedema  
Gingival swelling  
Gleich's syndrome  
Haemorrhagic urticaria  
Hand dermatitis  
Henoch-Schonlein purpura  
Henoch-Schonlein purpura nephritis  
Heparin-induced thrombocytopenia  
Hereditary angioedema  
Hereditary angioedema with C1 esterase inhibitor deficiency  
Hypersensitivity  
Hypersensitivity myocarditis  
Hypersensitivity pneumonitis  
Hypersensitivity vasculitis  
Idiopathic urticaria  
Immediate post-injection reaction  
Immune thrombocytopenic purpura  
Immune tolerance induction  
Implant site dermatitis  
Implant site hypersensitivity  
Implant site rash  
Implant site urticaria  
Incision site dermatitis  
Incision site rash  
Infusion related hypersensitivity reaction  
Infusion related reaction  
Infusion site dermatitis  
Infusion site eczema  
Infusion site hypersensitivity  
Infusion site rash  
Infusion site recall reaction  
Infusion site urticaria  
Infusion site vasculitis  
Injection related reaction  
Injection site dermatitis  
Injection site eczema  
Injection site hypersensitivity  
Injection site rash  
Injection site recall reaction

Jazz Pharmaceuticals Ireland Limited  
Statistical Analysis Plan – Protocol JZP458-201

Injection site urticaria  
Injection site vasculitis  
Instillation site hypersensitivity  
Instillation site rash  
Instillation site urticaria  
Interstitial granulomatous dermatitis  
Intestinal angioedema  
Iodine allergy  
Kaposi's varicelliform eruption  
Kounis syndrome  
Laryngeal oedema  
Laryngitis allergic  
Laryngospasm  
Laryngotracheal oedema  
Limbal swelling  
Lip oedema  
Lip swelling  
Mast cell degranulation present  
Medical device site dermatitis  
Medical device site eczema  
Medical device site hypersensitivity  
Medical device site rash  
Medical device site recall reaction  
Medical device site urticaria  
Mouth swelling  
Mucocutaneous rash  
Multiple allergies  
Nephritis allergic  
Nikolsky's sign  
Nodular rash  
Oculomucocutaneous syndrome  
Oculorespiratory syndrome  
Oedema mouth  
Oral allergy syndrome  
Oropharyngeal blistering  
Oropharyngeal oedema  
Oropharyngeal spasm  
Oropharyngeal swelling  
Palatal oedema  
Palatal swelling  
Palisaded neutrophilic granulomatous dermatitis

Jazz Pharmaceuticals Ireland Limited  
Statistical Analysis Plan – Protocol JZP458-201

Palpable purpura  
Pathergy reaction  
Perioral dermatitis  
Periorbital oedema  
Periorbital swelling  
Pharyngeal oedema  
Pharyngeal swelling  
Procedural shock  
Pruritus allergic  
Radioallergosorbent test positive  
Rash  
Rash erythematous  
Rash follicular  
Rash macular  
Rash maculo-papular  
Rash maculovesicular  
Rash morbilliform  
Rash neonatal  
Rash papulosquamous  
Rash pruritic  
Rash pustular  
Rash rubelliform  
Rash scarlatiniform  
Rash vesicular  
Reaction to azo-dyes  
Reaction to colouring  
Reaction to excipient  
Reaction to food additive  
Reaction to preservatives  
Red man syndrome  
Rhinitis allergic  
Scleral oedema  
Scleritis allergic  
Scrotal eczema  
Scrotal oedema  
Serum sickness  
Serum sickness-like reaction  
Shock  
Shock symptom  
SJS-TEN overlap  
Skin necrosis

Jazz Pharmaceuticals Ireland Limited  
Statistical Analysis Plan – Protocol JZP458-201

Skin reaction  
Skin test positive  
Solar urticaria  
Solvent sensitivity  
Stevens-Johnson syndrome  
Stoma site hypersensitivity  
Stoma site rash  
Swelling face  
Swelling of eyelid  
Swollen tongue  
Symmetrical drug-related intertriginous and flexural exanthema  
Therapeutic product cross-reactivity  
Tongue oedema  
Toxic epidermal necrolysis  
Toxic skin eruption  
Tracheal oedema  
Type I hypersensitivity  
Type II hypersensitivity  
Type III immune complex mediated reaction  
Type IV hypersensitivity reaction  
Urticaria  
Urticaria cholinergic  
Urticaria chronic  
Urticaria contact  
Urticaria papular  
Urticaria physical  
Urticaria pigmentosa  
Urticaria vesiculosa  
Urticarial dermatitis  
Urticarial vasculitis  
Vaccination site dermatitis  
Vaccination site eczema  
Vaccination site exfoliation  
Vaccination site hypersensitivity  
Vaccination site rash  
Vaccination site recall reaction  
Vaccination site urticaria  
Vaccination site vasculitis  
Vaccination site vesicles  
Vaginal exfoliation  
Vaginal ulceration

Jazz Pharmaceuticals Ireland Limited  
Statistical Analysis Plan – Protocol JZP458-201

Vasculitic rash  
Vernal keratoconjunctivitis  
Vessel puncture site rash  
Vessel puncture site vesicles  
Vulval eczema  
Vulval ulceration  
Vulvovaginal rash  
Vulvovaginal ulceration  
Vulvovaginitis allergic

